## 9.1.4.3 Early Termination

All subjects who completed or withdrew from the study received a telephone call for safety follow-up at 30 ( $\pm$  5) days after the last study visit unless they withdrew their consent for participation in the study. This telephone contact was made to assess if there were any AEs experienced since the last visit. In addition, the subject was asked about any new medications or changes in existing medications and the information was documented in the source documentation. The study site registered the contact in the interactive voice response system or interactive web response system.

The end of the study was the date of the last study visit for the last subject.

#### 9.2 DISCUSSION OF STUDY DESIGN

The study design, following well-characterized patients for 180 days after starting aripiprazole once monthly treatment, and retrospectively reviewing data regarding prior hospitalizations, psychiatric ED visits, and prior total psychiatric hospitalization days, was planned to allow the proposed hypotheses to be tested adequately.

By utilizing retrospective review of hospitalizations, each subject served as his or her own control. The 30-, 90-, and 180-day analyses allowed for relatively equivalent comparison of the previous 6-month data.

This was an open-label study with one treatment arm, therefore, no active or placebo control or randomization was used. Treatment bias was eliminated via the objective assessments employed.

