For subjects who were psychiatrically stabilized and discharged prior to the completion of the required 14-day course of oral aripiprazole, a pre-discharge assignment was given to a community support worker (CSW) or Study Coordinator (SC). The CSW/SC maintained regular contact with the subject until the first outpatient visit in Phase B (Week 2), when oral aripiprazole was discontinued. Regular contact was defined as no less than weekly, but could be more frequent depending on the clinical judgment of the CSW/SC and outpatient treatment team. Following the Week 2 Visit, subjects had contact with their assigned CSW/SC based on routine clinical care. Contact with the CSW/SC could be in person or by telephone, as clinically appropriate.

Note: All long-acting antipsychotics were excluded from use during the study; however, aripiprazole once monthly was allowed (See Table 1 for more information about Prohibited and Restricted Medications).

Final; 26 Feb 2018 Page 4 of 80

ClinicalTrials.gov Identifier: NCT02717130

Name of Sponsor: [name]. at Florida Atlantic University

Name of Product: Abilify Maintena®, aripiprazole

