## 9.4.4 Blinding

The study was not blinded.

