## 9.5.1.8 Efficacy Assessments – Clinical Outcome

## 9.5.1.8.1 Clinical Global Impression–Improvement

The efficacy of study medication was rated for each subject using the CGI-I scale. The rater or investigator rated the subject's total improvement whether or not it was due entirely to drug treatment. All responses were to be compared to the subject's condition at baseline of the appropriate phase. The CGI-I during Phase B would have been assessed relative to the subject's condition at the Phase B baseline visit. Response choices included: 0 = not assessed; 1 = very much improved; 2 = much improved; 3 = minimally improved; 4 = no change; 5 = minimally worse; 6 = much worse; and 7 = very much worse.

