#### 9.5.1.8.2 Clinical Global Impression—Severity

The severity of illness for each subject was rated using the CGI-S scale. To assess CGI-S, the rater or investigator answered the following question: "Considering your total clinical experience with this particular population, how mentally ill is the patient at this time?" Response choices included: 0 = not assessed; 1 = normal, not ill at all; 2 = borderline mentally ill; 3 = mildly ill; 4 = moderately ill; 5 = markedly ill; 6 = severely ill; and 7 = among the most extremely ill patients.

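### Section 9.2 says treatment bias was eliminated, but an unblinded, single-arm, before/after comparison cannot have that property; objective outcomes limit measurement bias only

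*Combined protocol and SAP*

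**What the plan says.** Section 9.2 (Discussion of Study Design) makes three statements in close succession. On the comparator: "By utilizing retrospective review of hospitalizations, each subject served as his or her own control". On the design: "This was an open-label study with one treatment arm, therefore, no active or placebo control or randomization was used". Then, as its only remark on bias: "Treatment bias was eliminated via the objective assessments employed". Section 9.4.4 adds: "The study was not blinded".

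The primary comparison (Section 9.7.1.9) sets the hospitalization rate in the 30 days before against the 30 days after, and counts the index admission in the earlier period. Section 9.7.2 accordingly gives the pre-switch rate in this study as 100%.

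Section 9.1.4.2 assigns a community support worker or study coordinator (CSW/SC) to subjects discharged before the 14-day oral course is complete. Until the Week 2 visit, "Regular contact was defined as no less than weekly" (also in the Synopsis); after that, contact follows routine care. All subjects attend eight scheduled visits, from Baseline to Week 24.

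**The concern.** Objectivity of an endpoint addresses one kind of bias: whether the event is recorded correctly regardless of who is looking. The claim in 9.2 is broader. It says bias in the treatment comparison is gone, although nothing in the design separates the drug from everything else that differs between the six months before and the six months after. Using subjects as their own controls removes stable subject characteristics and nothing that changes over time.

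What is at stake is the type of conclusion. Section 7.4 hypothesizes that the treatment would lower hospitalization rates, and 9.2 says the design allows the hypotheses to be tested adequately. A reader who accepts the bias sentence would take any fall in admissions as an effect of the drug. The comparison supports only the statement that admissions changed after a package of injection, study visits and support contact, in people enrolled at a crisis.

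**Working it through.** The sentence rests on no stated figure, so there is none to reproduce. The check is textual, with three illustrations of size.

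**1. What objective recording leaves in place**

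| Source of bias | What the document says | Removed by an objective endpoint? |
|---|---|---|
| Selection on the index admission; regression to the mean | Entry at an acute admission, with need for a therapy change and a prior psychiatric admission or ED visit (9.3.1, criteria 4, 5, 7); index admission counted in the pre-period (9.7.1.9) | No |
| Unequal ascertainment | Before: Medicaid/DMH search, or records and caregiver data (9.5.1.3). After: prospective source documents (9.1.4.2) | No; direction unknown |
| Study-provided visits and CSW/SC contact | Described only after the switch (9.1.4.2) | No |
| Unblinded judgement | CGI-I, PSP, AIMS, BARS and SAS rest largely on clinician rating (9.5.1.8, 9.5.1.9); no blinded or independent rater described | Not applicable: these outcomes are judgements |

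CGI-S, the planned covariate, is also a global judgement ("Considering your total clinical experience with this particular population, how mentally ill is the patient at this time"). It is scheduled at screening only, so knowledge of treatment matters less there.

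**2. Size of the selection problem**

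Inputs: N = 90 completers, pre-period rate 100%, two-sided alpha 0.05 (9.7.2). Treat the outcome as any admission in the window and use an exact McNemar test. This simplifies the planned repeated-measures ANCOVA. Every subject has a pre-period event, so discordant pairs run one way only: b = number not readmitted, c = 0, and p = 2 × 0.5^b.

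- b = 5: p = 0.0625
- b = 6: p = 0.03125

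The test therefore rejects when at least 6 of 90 are not readmitted. With no drug effect and an ordinary 30-day readmission rate q, b follows Binomial(90, 1 − q).

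| Assumed q | Apparent reduction | Probability of rejecting |
|---|---|---|
| 15% | 85 points | about 1.00 |
| 28% | 72 points | about 1.00 |
| 30% | 70 points | about 1.00 |
| 50% | 50 points | about 1.00 |
| 90% | 10 points | 0.90 |

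The document gives no untreated readmission rate for this population. The 15%, 28% and 30% are borrowed from 9.7.2, where they serve other purposes; 50% and 90% are assumed to stretch the range.

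**3. Overlap of weekly contact with the primary window**

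The 14-day oral course starts at the first injection. Discharge may come at any time after that (Table 3, note b), and the post window starts at discharge (9.7.1.1). If discharge is d days after the injection:

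overlap = max(0, 14 − d) days

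- d = 0: 14 of 30 days
- d = 7: 7 of 30 days (23%)
- d ≥ 14: 0 days, and the assignment rule does not apply

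No distribution of d is given.

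**4. What added visits and contact could do alone**

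Set selection aside and assume a 30% background rate, independent periods, 90 pairs and no drug effect. Suppose the added visits and contact multiply the post rate by RR. Then p10 = 0.30 × (1 − 0.30·RR), p01 = 0.30·RR × 0.70, D = p10 − p01, S = p10 + p01, and

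probability of rejecting = Φ[(D√90 − 1.96√S) / √(S − D²)].

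For RR = 0.8: p10 = 0.228, p01 = 0.168, D = 0.06, S = 0.396, giving 0.145. For RR = 0.9, 0.8, 0.7, 0.6 and 0.5 the results are 0.065, 0.145, 0.278, 0.462 and 0.665. The RR range is assumed; the document offers no figure.

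**The case against.** The strongest defence is that 9.2 is about hospitalizations, ED visits and hospital days. Read that way, the objective assessments are recorded events, and rater bias mainly touches CGI-I (secondary) and PSP and the extrapyramidal scales (exploratory). Section 9.7.1.9 already treats secondary and exploratory p-values as hypothesis-generating, and 9.4.4 is open about the lack of blinding. This stands as far as it goes: the rater argument is the lesser part. It does not rescue the sentence, because selection, ascertainment and added contact act on the recorded events themselves. No blinded adjudication of admissions or their cause is described. That admission decisions were made knowing the treatment follows from the open-label design but is not stated.

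A second defence is practical. Nine subjects were recruited and no formal analysis was done, so the sentence supported no reported efficacy result. That is correct and limits the consequence to the design rationale.

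A reader might take the CGI-I instruction to score improvement "whether or not it was due entirely to drug treatment" as evidence of unblinded rating. It is not: it asks for no attribution to the drug and is silent on who knows the treatment. The evidence for unblinding is 9.4.4.

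**Conclusion.** The sentence is wrong as written. Objective outcomes may reduce measurement bias; the other biases listed above remain. Selection on the index admission is the dominant one. Under the simplification and assumed rates in step 2, it alone makes a significant reduction close to certain over most of the range. The separate effect of visits and contact cannot be derived from the document.

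Two stronger readings are tempting and not supported. A reader might infer that extra contact fills about half of the 30-day post window (14/30 = 47%). That is a ceiling reached only by subjects discharged essentially at the injection. Others have less or none, and weekly contact, possibly by telephone, is a minimum of about two contacts. A reader might also infer that subjects had no community support before the switch. The document does not say. The sites were linked to community mental health centers, and only the study's own assignment and visits are known to be new.

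Nor does any of this show that the drug lacks an effect. It shows that the design cannot isolate one.

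**What to change.** In Section 9.2, delete the sentence and replace it with text to this effect:

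> Hospitalization and ED records may reduce measurement bias. The comparison remains open to selection on the index admission and regression to the mean, to different ascertainment before and after the switch, and to study visits and CSW/SC contact provided only after it. CGI-I, PSP and the extrapyramidal scales are unblinded clinician ratings. Any difference is a within-subject change under the whole package of injection, study visits and support contact, and is not attributed to the drug alone.

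Do not add an analysis by number of CSW/SC contacts. Assignment depended on early discharge, and frequency above the weekly minimum on clinical judgement (9.1.4.2), so the count is confounded by clinical state and could mislead in either direction.

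The change costs a few lines of text and touches no data, analysis or clinical rule. The downside is a weaker claim.

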# 9.3.1 Inclusion Criteria

Subjects must have met all of the following criteria to be included in this study:

- 1. Were able to provide written informed consent.
- 2. Were male and female subjects 18 to 65 years of age, inclusive, at time of informed consent

Final; 26 Feb 2018 Page 30 of 80

- 3. Had a current and confirmed diagnosis of schizophrenia as defined by DSM-5 criteria and a history of the illness for at least 6 months prior to screening from a reliable source (e.g., subject, family member, friend, caregiver, healthcare provider, or medical records)
- 4. Present at one of the selected inpatient units with acute psychotic symptoms for hospitalization at study entry
- 5. Had a clinically indicated need for a change in current antipsychotic therapy
- 6. Were on Medicaid with searchable claims data or were Medicaid-eligible
- 7. Had at least one inpatient psychiatric hospitalization or psychiatric ED visit within the 6 months prior to screening as confirmed through Medicaid or all available medical records and reliable data from caregivers
- 8. Had been previously prescribed oral antipsychotic treatment for at least a substantial portion of the 6 consecutive months prior to screening, with estimated duration of prescribed treatment within the 6 months prior to screening as determined by Principal Investigator discretion and confirmed through Medicaid or all available medical records and reliable data from caregivers
- 9. Had a history of response to antipsychotic treatment, with no history of clozapine treatment
- 10. Were able to understand the nature of the study and follow protocol requirements, including the prescribed dosage regimens, tablet ingestion, aripiprazole once monthly injection, and discontinuation of prohibited concomitant medications
- 11. Were able to read and understand the written word with a passing score of 4 to 6 (i.e., equivalent to seventh to eighth grade reading level for REALM-SF literacy assessment) in order to complete subject-reported outcomes measures
- 12. Were willing to accept a monthly injection
- 13. Were male and female subjects who were surgically sterile (i.e., have undergone orchiectomy or hysterectomy, respectively); female subjects who were postmenopausal for at least 12 consecutive months; or male and female subjects who agreed to use an approved form of birth control during study participation

#### 9.3.2 Exclusion Criteria

Subjects who met any of the following criteria were excluded from this study:

1. Had current psychotic symptoms that could be explained by a diagnosis other than schizophrenia, including schizophreniform disorder, schizoaffective disorder, major depressive disorder, bipolar disorder, delirium, dementia, amnestic or other cognitive disorders. Also excluded were subjects with borderline, paranoid, histrionic, schizotypal, schizoid, or antisocial personality disorder.

Final; 26 Feb 2018 Page 31 of 80

- 2. Prisoners or subjects who were involuntarily incarcerated, or were incarcerated in the past 7 months for any reason
- 3. Required potent cytochrome P450 (CYP)2D or CYP3A4 inhibitors or CYP3A4 inducers
- 4. Were allergic, intolerant, or unresponsive to prior treatment with aripiprazole or other quinolinones or had a history of hypersensitivity to antipsychotic agents
- 5. Had received electroconvulsive therapy within the 6 months prior to screening
- 6. Had a history of neuroleptic malignant syndrome or clinically significant tardive dyskinesia as assessed by the investigator
- 7. Had a current diagnosis of diabetes or known fasting triglyceride levels consistent with risk for pancreatitis
- 8. Met DSM-5 criteria for a current substance use disorder within 3 months prior to screening:
  - a. Ingestion of an identified substance alone may not have met the criteria for substance use diagnosis and therefore might not exclude the patient. Exceptions to this included the use of intravenous drugs within 3 months prior to screening.
  - b. Patients with a diagnosis of a substance use disorder greater than 3 months prior to screening may or may not have been still in remission even if they have had some sporadic use. They must have met DSM-5 criteria identified for the specific substance to be out of remission.
- 9. Received treatment with long-acting injectable antipsychotics (e.g., haloperidol decanoate, fluphenazine decanoate, risperidone long acting injection [Risperdal Consta®], paliperidone palmitate extended release injectable suspension [Invega® Sustenna®], olanzapine for extended release injectable suspension [Zyprexa® Relprevv™]), in which the last dose was within 7 months prior to screening. Prior use of aripiprazole was allowed, but must have been discontinued prior to the current hospitalization.
- 10. Had a significant risk of committing suicide based on history, routine psychiatric status examination, investigator's judgment, or who had an answer of "yes" on Question 4 or Question 5 within the last 30 days on the baseline version of the C-SSRS
- 11. Had a history or evidence of a medical condition that would expose them to an undue risk of a significant AE or interfere with assessments of safety or efficacy during the course of the study, including but not limited to hepatic, renal, respiratory, cardiovascular, endocrine, neurologic, hematologic, or immunologic disease as determined by the clinical judgment of the investigator
- 12. Had results from one or more of the following laboratory tests, vital signs, and ECG tests at screening that were exclusionary (laboratory testing and ECGs were performed locally):
  - a. Platelets  $\leq 75,000/\text{mm}^3$

Final; 26 Feb 2018 Page 32 of 80

- b. Hemoglobin  $\leq 9 \text{ g/dL}$
- c. HbA1c > 7.0% or fasting blood glucose > 126 mg/dL
- d. Neutrophils, absolute  $\leq 1000/\text{mm}^3$
- e. Aspartate transaminase (AST) > 3x ULN
- f. Alanine transaminase (ALT) > 3x ULN
- g. Creatinine  $\geq 2 \text{ mg/dL}$
- h. Diastolic blood pressure > 105 mmHg
- i. QTc > 475 msec on either the QTcB (Bazett) or QTcF (Fridericia) corrections on ECG, confirmed by a second tracing
- j. Any other abnormal laboratory tests, vital sign results, or ECG findings that, in the judgment of the investigator, were medically significant and would affect the safety of the subject or the interpretation of the study results. Abnormal results for laboratory parameters or vital signs were to be repeated to ensure reproducibility of the abnormality before excluding a subject based on the criteria noted above.
- 13. Had been previously enrolled in an aripiprazole once monthly clinical study
- 14. Had participated in any clinical study with an investigational agent within the past 30 days
- 15. Were pregnant or lactating

#### 9.3.3 Removal of Subjects from Therapy or Assessment

## 9.3.3.1 Entire Study

If the sponsor terminated or suspended the study for safety or unanticipated other reasons, prompt notification was to be given to Otsuka America Pharmaceutical, Inc. (OAPI), IRBs, and regulatory authorities in accordance with regulatory requirements.

#### 9.3.3.2 Individual Center

The sponsor was to notify OAPI promptly if the study is terminated by the sponsor or the IRB at the site.

#### 9.3.3.3 Individual Subject

If a subject discontinued from the study prematurely, the reason must have been fully evaluated and recorded appropriately in source documents and the CRF. If the subject was being withdrawn because of an AE, that AE should have been indicated as the reason for withdrawal.

Final; 26 Feb 2018 Page 33 of 80

An increase in suicidal ideation or homicidal ideation would result in withdrawal from the study, based on the investigators discretion.

All subjects had the right to withdraw at any point during treatment without prejudice. The investigator could discontinue a subject's participation in the study at any time if medically necessary. In addition, subjects meeting the following criteria were to be withdrawn from the study:

- 1. Occurrence of any AE, intercurrent illness or abnormality in a laboratory assessment which, in the opinion of the investigator, warranted the subject's permanent withdrawal from the study
- 2. Treatment with a prohibited concomitant medication other than the use of appropriate medications for the treatment of adverse events under direction of the investigator
- 3. Subject noncompliance, defined as refusal or inability to adhere to the study schedule or procedures per the investigator's discretion
- 4. At the request of the subject, investigator, OAPI or designee, or regulatory authority
- 5. Subject became pregnant
- 6. Subject was lost to follow-up

The sponsor notified OAPI promptly when a subject was withdrawn.

#### 9.4 TREATMENTS

#### 9.4.1 Treatments Administered

All active study drugs were provided by the manufacturer at no cost.

Aripiprazole once monthly and oral aripiprazole were prescribed and administered according to recommendations contained in their respective product labeling.

The following treatments were administered to subjects in this study:

- Aripiprazole, administered once monthly via gluteal or deltoid IM injection, as outlined in the product labeling
- Oral aripiprazole:
  - o Subjects in Phase A were administered oral aripiprazole to determine tolerability, based on the prescribing information

#### DOSAGE ADJUSTMENTS FOR MISSED DOSES OF ARIPIPRAZOLE ONCE MONTHLY

If the second or third doses were missed:

Final; 26 Feb 2018 Page 34 of 80

- If > 4 weeks and < 5 weeks elapsed since the last injection, the injection as administered soon as possible
- If > 5 weeks elapsed since the last injection, concomitant oral aripiprazole was restarted and given for 14 days with the next administered injection

If the fourth or subsequent doses were missed:

- If > 4 weeks and < 6 weeks elapsed since the last injection, the injection was administered as soon as possible
- If > 6 weeks elapsed since the last injection, concomitant oral aripiprazole was restarted and given for 14 days with the next administered injection

# 9.4.2 Identity and Storage of Drug Under Study(s)

All study drug was securely locked in a cabinet or enclosure according to the storage instructions on the product labeling. Access was limited to the investigators and their designees. Neither investigators nor any designees were allowed to provide study drugs to any subject not participating in this protocol.

# 9.4.3 Method of Assigning Subjects to Treatment Groups

A total of 177 subjects were planned to be enrolled in the study. Subjects were assigned a subject ID number chronologically based on the order of enrollment into the study. The study was a single-arm, nonrandomized study.

## 9.4.4 Blinding

The study was not blinded.

#### 9.4.5 Prohibited Medication

During the Screening Period, subjects could be treated with any oral antipsychotic of the clinician's choice, with the exception of clozapine and olanzapine. However, oral olanzapine was permitted during the Screening Period only for subjects who are eligible for Phase A.

Following the concomitant 14-day oral lead-in in Phase B after the first injection of aripiprazole once monthly, oral aripiprazole was the only allowed rescue medication. Subjects requiring any other antipsychotic medications except for oral aripiprazole for rescue during Phase B of the study after the first 14 days were discontinued.

A summary of medications that are prohibited or restricted prior to screening or during the study is provided in Table 1.

Final; 26 Feb 2018 Page 35 of 80

